1.2 Funding and Support in kind

FUNDER(S)	FINANCIAL AND NON
	FINANCIALSUPPORT GIVEN

Stroke Implementation Group	Financial Support during the implementation phase		

1.3 Role of Study Sponsor

The sponsor of this study is Cardiff University (CU). It is the role of the sponsor to confirm that there are proper arrangements to initiate, manage, monitor, and finance a study. The sponsor will not play a role in the study design, conduct, data analysis and interpretation, manuscript writing, or the dissemination of results; this will be the responsibility of the Chief Investigator, [name], an employee of the sponsor organisation.

The sponsor has responsibility for overall oversight of the trial. The role of the Sponsor is to ensure the study is run safely and effectively by requiring the following:

- Proportionate peer review
- Provision of all appropriate, valid supporting documentation at the point of application
- Clear definition of roles and responsibilities of organisations and individuals, signed off prior to the study commencing
- Appropriate level of monitoring and audit
- A risk assessment process to identify any potential risks to the organisation or the health, safety, and well-being of researchers and research participants
- Involvement of patients and/or the public in study design, where appropriate
- The Chief Investigator's suitability to fulfil their role, through relevant experience and appropriate training
- Provide guidance in relation to the required ethical and/or other regulatory approvals that may be required
- Provide assurance of adequate indemnity/insurance for design, management and conduct of the study
- Dissemination of study findings in an appropriate manner

The Sponsor, through their Research and Development department, has a veto on overall approval for the study.

The funder's role is to finance the study and to receive a study report.

1.4 Protocol Contributors

The protocol has been written by Professional Doctorate student [name] and has been reviewed and revised by [name] and [name], the student's supervisors. Health Professionals employed by Aneurin Bevan University Health Board, groups associated with the Gwent Public Service Board, and Carers

and individuals with lived experience have provided further input through consultation.

KEY WORDS:

Cardiovascular Disease

Equality Health Advisor

Pilot Study

Health Behaviours

Peripheral Vascular Disease

Psycho-social factors

Physiological impacts

Stroke

Transient ischaemic attack

Wider determinants of health

2. ABBREVIATIONS

CI	Chief Investigator
CRF	Case Report Form
EHA	Equality Health Advisor
GCP	Good Clinical Practice
GP	General Practitioner
ICF	Informed Consent Form
ICH	International Conference of Harmonisation
ISF	Investigator Site File
HCRW	Health and Care Research Wales
HRA	Health Research Authority
NHS	National Health Service
PI	Principal Investigator
PIS	Participant Information Sheet
R&D	Research & Development Office
REC	Research Ethics Committee

RN	Research Nurse
SOG	Study Operational Group
SMG	Study Management Group
SPT	Study Project Team
TMF	Trial Master File

3. BACKGROUND AND RATIONALE

Cardiovascular disease and stroke are common causes of mortality and morbidity in the United Kingdom (UK) (Biobank 2023) and carry a high economic burden (Gheorghe et al. 2018; Patel et al. 2019). Cardiovascular disease and stroke can impact people of all backgrounds, but health disparities are more prominent in those of low sociodemographic and ethnic groups (Razieh et al. 2022). These groups tend to experience poorer health outcomes and are more likely to be impacted (Stack et al. 2020; Eastwood et al. 2021; Razieh et al. 2022). Currently, cardiovascular disease and stroke cost the National Health Service (NHS) and wider economy some £55.1 billion per year (Luengo-Fernández et al. 2006; Patel et al. 2019)

Peripheral vascular disease (PVD) is the third leading cause of atherosclerotic morbidity following coronary heart disease and stroke (Criqui et al. 2021). Research suggests those diagnosed with PVD are vulnerable to more severe cardiovascular events (Grenon et al. 2013). Furthermore, PVD shares several risk factors with atrial fibrillation, with a credible link to an increased risk of stroke (O'Neal et al. 2014)

To reduce incidences of cardiovascular disease, stroke and peripheral vascular disease preventative measures such as lifestyle modifications and risk factor management have proven to be effective (Sarikaya et al. 2015; Rippe 2019; King et al. 2022; Ghodeshwar et al. 2023) However, their effectiveness may be limited due to various challenges (Bailey 2016). Evidence shows social gradient and social determinants of health (SDoH) as key denominators of health and wellbeing and has informed policy in recent years (Michael Marmot 2010; Michael Marmot 2020).

However, despite efforts in achieving equitable improvements to health across all social gradients, progress is proving difficult in the current social, economic, and political environment, (Adler and Newman 2002; Carey and Crammond 2015; Solutions 2021). Considering the complexities influencing health inequalities, a one size fits all approach seldom succeeds (Matheson 2020) (NHS-England 2022). Thus, leading to targeted policies addressing social determinants of health exposing bleak deliverable outcomes (Lee et al. 2018).

Public Health Wales (PHW) supports strategies to improve population health advocating that all public bodies pursue a collective response to new ways of working (PHW 2022). This places the NHS in a unique position as an anchor institution to tackle social determinants of health, intently endorsed across the UK's four devolved nations (nhsconfed 2021; NHS-England 2022)

The health burden of cardiovascular disease, stroke and peripheral vascular disease on patients, caregivers, the health system, and the broader economy, is substantial – resulting in markedly reduced ability to perform activities of daily living, poor health-related quality of life, high rates of unplanned hospitalisations, excessive costs, and premature mortality (Roth et al. 2020; Portas et al. 2022)

In contrast to lifestyle modifications and risk factor management therapies provided by primary and secondary care NHS provision (Riley et al. 2015), in the effort to address social determinants of health, there is limited research in evidence-based interventions that captures and acts upon adverse social determinants of health, such as food and housing insecurity, or exposure violence and poverty (Kreuter et al. 2021; Powell-Wiley et al. 2022)

[name] Marmot provides subtle clarity in his book the Health Gap (Marmot 2017) to support modifications to health practice:

"Why treat people and send them back to the conditions that made them sick?" p4

The NHS, in particular Aneurin Bevan University Health Board perhaps can support their local community in the attempt to reduce health inequalities and social determinants of health. The recently published Building a Fairer Gwent: improving health equity and the social determinants report (Michael Marmot 2023) confirms this call for action. Therefore, there is an urgent need for tailored interventions to help people to live the life they wish to live rather than a life dictated to them because of their circumstances. In this study the target population are those diagnosed with a vascular condition. The aim is to explore if a targeted place-based Health and Wellbeing Improvement Intervention using the UK Government endorsed adapted Labonte model is feasible and acceptable to intervention providers and stakeholders.

Why this research is important for the public/patients/healthcare services

National Institute for Health and Care Excellence (NICE) guidance states reducing health inequalities is part of its core principles (NICE 2023). However, scepticism in effective NHS deliverables to address healthcare inaccessibility and poor healthcare quality, wider determinants of health and negative health behaviours is recognisable (Attree et al. 2012; Asaria et al. 2016)

People justification

Research indicates that the largest health disparities are experienced by members of the most socially disadvantaged communities. Evidence suggests, the most socially disadvantaged people live with long-term conditions earlier, accumulate them more quickly, and endure them longer (Michael Marmot 2010; Bambra et al. 2020; Michael Marmot 2020). This establishes a moral requirement for the NHS and wider partners to actively seek novel social and health-related interventions that may alleviate health and wellbeing outcomes.

Business and economic justification

The most socially disadvantaged individuals and localities command a higher expenditure per capita than the wealthiest with longer lifespans, despite living shorter lives and more years spent in poor health. Excessive costs for healthcare can be attributed to the use of pharmacological therapy, hospital emergency room visits, extended hospital stays, postponed discharges, and pressure on elective care (McCabe et al. 2017). How health inequality affects the fall in economic productivity is a further cause for concern. According to a modelling analysis by the Health Foundation, by 2040, one in five people will live with one or more major illnesses (Watt 2023). This establishes a business case to improve outcomes in population health with the aim to potentially reduce and repurpose cost savings for social and economic benefit.

[figure not shown]
Healthcare quality

There is a clear intersection between patient safety and health inequalities, manifesting itself in communication breakdown, deterring marginalised ethnic groups from seeking timely medical attention (Chauhan et al. 2020). Poorer members of society lack access to digital tools, increasing the likelihood of missed appointments and access to timely treatments. Healthcare services providing a one size fits all pathway, coinciding with unequal risks of harm between different ethnic population groups (Wade et al. 2022). A recent report published by the NHS Race and Health Observatory claims ethnic health inequality is prominent and further work to address inequalities such as improving the quality of ethnicity data and increased investment in community engagement (King'sFund 2021). It is evident, health needs of the UK population are changing (McKee et al. 2021) in terms of prevention and treatment of illness and disabilities. Thus, providing an ethical stance to make improvements to a care model.

Research seems prominent in its commitment to understand what approaches the NHS is taking to address inequalities (Dorling et al. 2016; Brennan et al. 2023). However, there seems a lack of comprehensive research focusing specifically on test and learn interventions that may reduce inequalities for those in the secondary care system, using a place-based approach. In short, knowledge of health inequalities and the benefits of addressing social determinants of health is evident, but evidence of interventions that bring about significant change is limited (McGowan et al. 2021; PublicHealthEngland 2021; Maria Luisa Buzelli and Alderwick 2022).

Faced with a high unmet need for effective interventions to reduce inequalities in outcomes, experience, and access, NICE (NICE 2023) recommends applying place based approaches considering factors identified in the UK government advocated adapted Labonte model.

Figure 1: Adapted Labonte model

Source: Public Health England. Adapted Labonte model Place-based approaches for reducing health inequalities: accessed on 06/12/2023

This model aims to simplify the causes of health inequalities in what is deemed a complex system. The adapted Labonte model considers lifestyle drift, drawing attention to wider determinants that shape health behaviour and influence change (Cohn 2014; Carey et al. 2016).

Building a Fairer Gwent (Michael Marmot 2023) report advocates universal interventions in every area of Gwent with provision developed more intensely where need is higher. The report provides evidence that more targeted interventions are needed.

By focusing on inequalities and inequities of wider determinants of health, improving health behaviours, checking physiological status, and addressing psychosocial factors the EQUALITY HEALTH-CVD pilot study intention is to compliment these priorities as a test and learn project. The study aims to understand if the EQUALITY HEALTH-CVD pilot study is accepted to those diagnosed with a vascular condition. The study has the potential to benefit a larger community by providing a more targeted approach to individuals who require more care. In contrast, this study will be accessible to participants from all social backgrounds and descriptive analysis of social economic factors will be discussed to inform future research.

4. OBJECTIVES AND OUTCOME MEASURES/ENDPOINTS

RESEARCH QUESTION/AIM(S)

Aim: To test the feasibility and acceptability of a secondary care place-based intervention using a pilot study. The intervention focuses on four dimensions linked to the Labonte model.

- 1. Physiological impacts Health Check
- 2. Health behaviours Health Coaching
- 3. Psycho-social factors Community and public service assets
- 4. Wider determinants of health Community and public service assets

Questions:

- 1. Is the Intervention feasible and acceptable in terms of recruitment and attrition?
- Is it feasible to implement the intervention?
 (e.g., number and duration of contact visits, completion of data collection, completion of four intervention components, and number of community and public service assets offered, description of social background)
- 3. What are the participants perceived experiences and perceptions of the intervention?
- 4. What are the deliverers perceived experiences and perceptions of the intervention, including barriers and facilitators to delivery and perceived impacts?

Objectives

Primary Objective

To test the feasibility and acceptability of a secondary care place-based intervention focusing on four dimensions linked to the Labonte model.

- Physiological impacts Health Check
- 2. Health behaviours Health Coaching
- 3. Psycho-social factors Community and public service assets
- 4. Wider determinants of health Community and public service assets

Outcome Measures/Endpoints

- 1) To determine effective means of recruiting participants (recruitment and attrition)
- 2) To assess the feasibility of implementing the intervention (e.g number and duration of contact visits, completion of four intervention components, completion of data collection and number of community and public service assets offered, description of social background)

When, Who and How

Baseline, RN – CRF A and questionnaires
1 week EHAEquality Health Home Visit form
4 weeks EHA
Equality Health Home Visit form

	8 weeks EHA Equality Health Home Visit form
	12 weeks EHA Equality Health Home Visit form, questionnaire
Secondary Objectives	To explore the participants acceptability and perception of the
To explore the participants acceptability and perception of the intervention	intervention
Evalore the deliverers acceptability of the	2. Explore the deliverers
Explore the deliverers acceptability of the intervention, including barriers and facilitators to delivery and perceived	acceptability of the intervention, including barriers and facilitators to delivery and perceived impacts.
impacts.	When, Who and How
	12 weeks researcher - interview
	CRF B and questionnaires

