9. STUDY PROCEDURES

Schedule of assessments (0 month)

Participants in the study will undergo eligibility screening in three different settings. During emergency admission in GUH, as an inpatient at YYF or during a routine clinic at various sites. The participants care team will provide potential participants with a patient information sheet.

Baseline data

All participants will be consented by a delegated member of the ABUHB research delivery team. After consent the following questionnaires will be completed

- CASE REPORT FORM A
- PROMIS 10
- EQ-5D
- South Wales Social Wellbeing Scale

The questionnaires will be collected either by Microsoft forms if Wi-Fi is available or paper form and then transferred to an excel database.

The initial consultation of the intervention date and time be organised either during baseline data collection by the ABUHB research delivery team, or via telephone or email by the Equality Health Advisor.

(Follow Up 1) Equality Health- CVD Intervention (week 1) Initial Consultation

Consented Participants will be offered an initial face to face home based appointment where the Equality Health Advisor will provide place-based support focusing on four domains.

- 1. Physiological impacts
- Health behaviours
- 3. Psycho-social factors
- 4. Wider determinants of health
- **1.**The Equality Health Advisor will conduct the following physical tests:
- Blood Pressure and HR
- Height
- Weight
- BMI
- Waist Circumference

All physical test results will be recorded - if blood pressure is considered high: Hypertension: Systolic 140 mm Hg or higher or diastolic 90 mm Hg or higher the Equality Health Advisor will advise the participant to keep track of their blood pressure at home using an automated blood pressure monitor once a day at a different time of the day for a period of seven days. If blood pressure remains high after this time the participant will be advised to seek medical support at their registered GP surgery. If the participant does not own a blood pressure monitor, a monitor recommended by the British and Irish Hypertension Society blood pressure will be provided to the participant by the study team.

If a blood pressure reading is in the category of hypertensive crisis (180/100) the Equality Health Advisor will advise the participant to seek immediate medical support.

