9.1. Recruitment

20 participants will be recruited over a 4-to-8-month period. The aim is to recruit a conservative 5 participants per month for a total of 4 months to reach a target recruitment of 20 participants. The following routes of recruitment will be used: Potential participants will be identified locally at sites across Aneurin Bevan University Health Board by cardiovascular disease, peripheral artery, and stroke specialists. Including emergency admission, in patient setting or consultant and nurse lead clinics.

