9.2. Screening and Eligibility Assessment

Initial identification and eligibility of participants will be confirmed by the clinical team and supported by delegated ABUHB research delivery team.

Potential participants will obtain a Participant Information Sheet (PIS) (via various routes including in hospital setting, at a clinical appointment or posted out with the potential participants outpatient appointment letter.

Electronic screening logs will be kept and will include reason for non-participation. The reason for non-participation will be sought via the ABUHB research delivery team.

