12. STATISTICS AND ANALYSIS

12.1. Description of Statistical Methods

Questionnaires

The researcher will analyse and report response and completion rates to questionnaires, in addition to summarising descriptive variability in questionnaire outcomes.

Participant and Equality Health Advisor Interviews

Analysis of interview data will follow Braun and Clarke's thematic method and will include

- Data collection
- Data Management (using qualitative software)
- Data Analysis (familiarisation, generating codes, searching for theme, defining ad naming themes)
- Illustrative quotes will support findings

Equality Health Advisors Reflective Diaries

Analysis of reflective diaries will help understand the thoughts, feelings and experiences documented by the Equality Health Advisors over the study time period. These accounts will support findings

These points of interest are aimed to identify insights and problems that may occur before considering a full RCT.

Progression criteria

To recognise and acknowledge protocol success the following criteria will be applied using a green light system.

Criteria Progression	Green Light	Amber Light	Red Light
	Recruitment	and Attrition	
No of participants offered the intervention and declined uptake during the consent process	≤ 20%	≤ 50-74% Investigate reasons for refusal	≤ 75% Use Modify intervention Using 6 SQUID (Six-Step Quality Improvement Design)
Recruitment Rate	≥ 80% of the target number of participants recruited within the first 5 months.	50-79% of the target number recruited within the first 5 months. Implement additional recruitment strategy	49-0% of the target number recruited within the first 5 months. Reevaluate recruitment strategies and consider protocol modifications
Attrition Rate at the end of the study	25% Drop out Consider progression to RCT	Investigate reasons for dropout and implement retention strategies	75-100% Consider not proceeding with RCT funding bid submission
Follow up Completion	90-100% of participants complete the scheduled number of contact visits.	60-89% of participants complete the scheduled number of contact visits. Investigate barriers and enhance follow-up procedures.	< 75% of participants complete the scheduled number of contact visits Re-evaluate follow up strategy and consider protocol adjustments when considering future research.

Feasibility of Implementing the Intervention			

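### Primary objective 1 asks for effective means of recruiting, but no stated measure is by route, and the uptake criterion leaves people who never respond out of its numerator

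*Protocol*

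**What the plan says.** The first outcome under the primary objective in Protocol section 4 is "To determine effective means of recruiting participants (recruitment and attrition"). The study summary in section 1.1 lists the same item as primary objective 1.

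People can be reached in several ways. Section 9 states "Participants in the study will undergo eligibility screening in three different settings". Section 9.1 describes the routes as "Including emergency admission, in patient setting or consultant and nurse lead clinics". Section 5 lists five sites. Under section 9.2 the information sheet may be handed over in hospital or at a clinic appointment, or "posted out with the potential participants outpatient appointment letter". Under section 9.3 a patient may take the sheet home and contact the research nurse later.

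On measurement before consent, section 9.2 says "Electronic screening logs will be kept and will include reason for non-participation". Section 6 sends a summary of these logs to the Study Operational Group. The progression table in section 12.1 has two rows on recruitment:

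- uptake: "No of participants offered the intervention and declined uptake during the consent process", green at 20% or below, amber from 50 to 74%, red at 75%;
- recruitment rate: green if at least "80% of the target number of participants recruited within the first 5 months".

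The data-source list in section 4 starts at baseline with Case Report Form A, which is completed after consent.

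**The concern.** An objective about means of recruiting needs at least a count by means. None is stated: both recruitment rows are overall figures, and the log description does not name route. This is hard to leave to a later analysis document. Route has to be written down when the person is approached, and for someone who never consents there may be no other record from which to recover it.

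The second part concerns the uptake row. It counts refusal during the consent process. A person who is posted a sheet, or takes one home, and is not heard from again has not refused in that process. That person cannot be in the numerator, and because being offered is undefined, may or may not be in the denominator. The row feeds a traffic-light decision made ahead of a possible full RCT, so a loose definition could change the colour.

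**Working it through.** **The plan's own figures.** Section 9.1 states "The aim is to recruit a conservative 5 participants per month for a total of 4 months to reach a target recruitment of 20 participants". 5 × 4 = 20, which agrees with the stated target. The green line for recruitment rate is 0.80 × 20 = 16 recruited by month 5. Both are totals, and neither says anything about a route.

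**Objective against measures**

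| Source | What it supplies | By route? |
|---|---|---|
| Section 4 data-source list | Data from baseline onward | No pre-consent source named |
| Section 9.2 screening log | Includes reason for non-participation | Route not named as a field |
| Section 6 report to the Study Operational Group | Log summary, numbers recruited | Not stated |
| Section 12.1 uptake row | One decline rate | No |
| Section 12.1 recruitment-rate row | Share of target by month 5 | No |

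**What a pooled rate can hide (assumed counts).** Declines of 0/10, 2/12 and 3/3 in three settings pool to 5/25 = 20%. So do 1/8, 1/8 and 3/9. The row reads the same in both cases.

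**Effect of silent non-response (assumed counts).** The protocol gives no number approached. Take c = 20 consenting (the target), d = 5 refusing at consent, and k people who receive a sheet and never respond.

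- Refusals only, with non-responders left out: d/(c + d) = 5/25 = 20%, green for every k (exact 95% interval 7% to 41%).
- Non-responders counted as not taken up: (d + k)/(c + d + k) = (5 + k)/(25 + k).

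| k | Calculation | Rate |
|---|---|---|
| 0 | 5/25 | 20% |
| 10 | 15/35 | 43% |
| 15 | 20/40 | 50% |
| 20 | 25/45 | 56% |
| 40 | 45/65 | 69% |
| 55 | 60/80 | 75% |

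With 20 consenting, only the total d + k matters for the second rate. Green allows at most 5 non-consenters of any kind (5/25). 50% is reached at 20 (20/40) and 75% at 60 (60/80). The printed table assigns no colour between 20% and 50%; that is a separate matter.

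**Precision of a by-route report.** With 8 or 9 people offered per setting, 1/8 declining has an exact 95% interval of 0% to 53%, and 3/9 has 7% to 70%.

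**The case against.** Several points on the other side have force.

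- A reader might infer that the refusal rate is the only recruitment measure. It is not: there is the recruitment-rate row, the log with reasons for non-participation, and its summary to the Study Operational Group. This stands, although none of these is stated by route.
- A reader might infer that routes cannot be compared at all. The documents do not support that. The log is said to include reasons, which is not a closed list, and staff may record route anyway. What can be said is that nothing requires it.
- The objective carries its own gloss of recruitment and attrition, and question 1 in section 4 asks only about those. No comparison of routes is promised. That is a fair reading, but the words about effective means still appear as a primary objective without a matching measure.
- A reader might infer that the uptake figure is too favourable whenever sheets are posted. That is not established. The sheet goes out with a clinic appointment letter, so many recipients will be met in person and can consent or decline there. Those lost would mainly be non-attenders, people not approached, or people who took the sheet home and did not come back.
- Non-responders are not shown to be missing from the log, nor from the denominator. The protocol neither includes nor excludes them. Only their absence from the numerator follows from the wording.
- Full eligibility, including capacity and willingness to be interviewed, may be unknown for someone never met. The denominator in any fix must allow for this.

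The possibility that a statistical analysis plan specifies a by-route table does not settle the point, because such a table depends on the log holding route from the start.

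**Conclusion.** The point holds in a limited form. Primary objective 1 has no matching measure by route. The uptake row, as worded, leaves passive non-uptake out of its numerator and does not define who counts as offered, so it can look too favourable.

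The size is unknown. The shift from 20% to 50% rests on assumed counts of 20 consenting, 5 refusing and 15 silent; no figure in the protocol bears on the number silent. The intervals above show that 20 participants cannot establish which route is best, so the gain from recording route is description, in keeping with the descriptive analysis that section 1.1 plans. The change is worth making before recruitment because it is cheap and the information may not be recoverable afterwards.

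**What to change.** 1. In section 9.2, require the existing screening log to hold, for everyone given or sent an information sheet: setting and site, mode of approach (in hospital, at clinic, by post), and outcome (consented, declined, no response, ineligible).
2. In section 12.1, add one descriptive table of these counts by route, without a claim to determine which route is best at this sample size.
3. Redefine the uptake row as not consented among all those offered and not known to be ineligible. State that being offered means having been given or sent a sheet, and show active refusals and non-response separately so that missed contact is not read as refusal.

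If the team does not intend to describe routes, objective 1 could instead be reworded to overall recruitment and attrition, in line with question 1 in section 4. The uptake row would still need its denominator defined.

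The cost is a few extra log columns, one table, and an uptake figure that may look less favourable.
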